#### **2.4.5 Analyses of safety data**

The summary of safety results will be presented by treatment group.

##### ***General common rules***

All safety analyses will be performed on the safety population as defined in Section 0, unless otherwise specified, using the following common rules:

- The baseline value (with the exception of lab parameters, like eGFR and HbA1C) is defined as the last available value before the first dose of double-blind IMP. Baseline eGFR, HbA1C and other lab parameters values are the values assessed by the central laboratory at randomization visit.
- There will be no imputation of missing values for clinical laboratory test results, vital sign measurements in the safety analyses and there will be no hypothesis testing for results from safety analyses.
- All measurements, scheduled or unscheduled, fasting or not fasting, will be assigned to analysis windows defined in Section 2.1.4.

##### ***2.4.5.1 Analyses of adverse events***

###### ***Generalities***

###### ***Analysis of treatment-emergent adverse events***

The following summaries of treatment emergent adverse events will be generated for the safety population.

- Overview of TEAE, summarizing number (%) of patients by treatment group with any
  - TEAE
  - Serious TEAE
  - TEAE leading to death
  - TEAE leading to permanent treatment discontinuation
- All TEAEs by primary SOC and preferred term
- All TEAEs related to IMP by primary SOC and preferred term

###### ***Analysis of treatment-emergent serious adverse events***

- All treatment-emergent SAEs by primary SOC and preferred term
- All treatment-emergent SAEs related to IMP by primary SOC and preferred term

***Analysis of treatment-emergent adverse events leading to permanent discontinuation***

- All TEAEs leading to permanent discontinuation by primary SOC and preferred term
- All TEAEs leading to death by primary SOC and preferred term

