### **10.3.1 Temporary treatment discontinuation with investigational medicinal products**

All IMP discontinuation should initially be considered as temporary unless permanent discontinuation is mandated by the protocol (see [Section 10.3.3](#)), and the Investigator should make best effort to resume IMP treatment as early as practically possible. There is no defined limit to the duration of temporary discontinuation. This is in part due to the fact that a patient is expected to participate in the study for a period potentially lasting several years. Reinitiation of treatment with the IMP will be done under close and appropriate clinical and/or laboratory monitoring once the Investigator is satisfied that, according to his/her best medical judgment, the IMP was unlikely to be responsible for the event concerned.

Temporary treatment discontinuation may be considered by the Investigator because of suspected AEs. Lower extremity complications (such as skin ulcers, infection, osteomyelitis, and gangrene) requiring treatment should lead to temporary discontinuation of IMP.

If DKA is suspected or confirmed, study treatment should be stopped immediately and should not be re-started unless another cause for the ketoacidosis is identified and resolved.

In addition, IMP administration should be stopped in patients admitted to the hospital for major surgical procedures or due to serious illness.

If a patient who is on an ACE-i/ARB does not tolerate the combination of the ACE-i/ARB with IMP due to hypotension/volume depletion, and one of the two agents (either the ACE-i/ARB or IMP) needs to be withheld, the ACE-i/ARB should be maintained, and the IMP should be withheld (temporarily if possible).

Reinitiation of treatment with the IMP will be done under close and appropriate clinical/and or laboratory monitoring once the Investigator is satisfied that, according to his/her best medical judgment, the responsibility of the IMP in the occurrence of the concerned event was unlikely.

Temporary discontinuation of IMP due to intolerance should be followed by reinitiation of 1 tablet of IMP qd (sotagliflozin 200 mg/matching placebo). Temporary discontinuation for any other reason should be followed by reinitiation of IMP at the last dose tolerated prior to discontinuation where possible.

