For all confirmed temporary treatment discontinuations, the start date and end date of the period with no IMP treatment should be recorded by the Investigator in the appropriate pages of the e-CRF. Additionally, temporary discontinuation should be recorded in the IRT.

Patients who temporarily discontinue IMP should be reassessed at every visit to determine whether it is possible to safely resume IMP. If a decision has been made that the discontinuation is

permanent, then the patient should be considered as permanently discontinued and the corresponding e-CRF page should be completed. Please note that permanent discontinuation should be a last resort.

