#### **10.4.3 General guidelines for reporting adverse events**

- All AEs, regardless of seriousness or relationship to IMP, spanning from the signature of the ICF until the end of the study as defined by the protocol for that patient, are to be recorded on the corresponding page(s) or screen(s) of the e-CRF.

- For this study, an endpoint assessment/adjudication committee is in place. This committee reviews important endpoints reported by the Investigators to determine whether the endpoints meet protocol-specified criteria. This is a periodic process, occurring after internal processing of the reported event (endpoint). The event as categorized by the Investigator will remain as such, even if judged differently by the adjudication committee later.
- Whenever possible, diagnosis or single syndrome should be reported instead of symptoms. The Investigator should specify the date of onset, intensity, action taken with respect to IMP, corrective treatment/therapy given, additional investigations performed, outcome, and his/her opinion as to whether there is a reasonable possibility that the AE was caused by the IMP or by the study procedure(s).
- The Investigator should take appropriate measures to follow all AEs until clinical recovery is complete and laboratory results have returned to normal, or until progression has been stabilized, or until death, in order to ensure the safety of the patients. This may imply that observations will continue beyond the last planned visit per protocol, and that additional investigations may be requested by the monitoring team up to as noticed by the Sponsor. At the prespecified study end-date, patients who experience an ongoing SAE or an AESI should be followed until resolution, stabilization, or death and related data will be collected.
- When treatment is prematurely discontinued, the patient's observations will continue until the end of the study as defined by the protocol for that patient.
- Laboratory, vital signs or ECG abnormalities are to be recorded as AEs if they are medically relevant based on the Investigator's medical judgement:
  - Symptomatic and/or
  - Requiring either corrective treatment or consultation, and/or
  - Leading to IMP discontinuation or modification of dosing, and/or
  - Fulfilling a seriousness criterion, and/or
  - Defined as an AESI

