## Adverse events leading to permanent treatment discontinuation

All TEAEs leading to permanent treatment discontinuation will be summarized and presented as number (%) of patients in each treatment group.

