## **2.2 DISPOSITION OF PATIENTS**

Screened patients are defined as any patients who signed the informed consent.

Randomized patients consist of all patients with a signed informed consent form who have had a treatment kit number allocated and recorded in the IRT database, regardless of whether the treatment kit was used. These patients form the randomized population.

For any patient randomized more than once, only the data associated with the first randomization will be used in any analysis population. The safety experience associated with any later randomization will be assessed separately. Patients who are not randomized will not be in the safety population.

For patient study status, the total number of patients in each of the following categories will be presented in the clinical study report using a flowchart diagram or summary table:

- Screened patients
- Screen failure patients and reasons for screen failure
- Nonrandomized but treated patients
- Randomized patients

- Randomized but not treated patients
- Randomized and treated patients
- Patients who complete the study treatment period as per protocol (as per e-CRF treatment status form)

Note: patients who die while on treatment will be treated as treatment completers

- Patients who discontinued study treatment by main reason for permanent treatment discontinuation (as per e-CRF treatment status form)
- Patients who complete the study as scheduled (i.e. subject status is death or completed on the Completion of end of study eCRF form or a study close-out visit was performed through alternative contact during the study close-out period)
- Patients who did not complete the study as scheduled and the reasons for study discontinuation
- Status at last study contact (as per e-CRF Subjects Status form)
- Patients who had known vital status during the study close-out period

Patients randomized but not treated will be included in the efficacy analysis.

The number (%) of patients who prematurely discontinued the study for primary efficacy events will be summarized. The main reason for study discontinuation will be summarized overall and according to whether or not the patients had a primary efficacy endpoint prior to study discontinuation. A patient will be considered as having discontinued the study for CV death, HHF, or urgent HF visit if the date of the last information on this endpoint (presence or absence) is before his/her scheduled Study Closeout Visit.

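### The SAP tabulates non-fatal AEs by action on IMP only for permanent discontinuation and counts up-titration in one arm only, so treatment-limiting intolerance short of a permanent stop is not compared by arm

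*SAP*

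**What the plan says.** **Planned tables.** Section 2.4.5.1 of the SAP has an overview line for any "TEAE leading to permanent treatment discontinuation" and one detailed table, "All TEAEs leading to permanent discontinuation by primary SOC and preferred term". The only other tables there defined by the outcome of an event are for TEAEs leading to death. Protocol 11.4.3.1 has the same limit: "All TEAEs leading to permanent treatment discontinuation will be summarized and presented as number (%) of patients in each treatment group". Disposition in SAP 2.2 likewise lists "Patients who discontinued study treatment by main reason for permanent treatment discontinuation" and has no category for patients in a temporary stop.

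**Handling of intolerance.** Protocol 10.3.1 states: "All IMP discontinuation should initially be considered as temporary unless permanent discontinuation is mandated by the protocol". It adds: "There is no defined limit to the duration of temporary discontinuation". Protocol 10.3 asks that a reduction from two tablets to one be considered before a temporary stop, and treats permanent discontinuation as the option to use last.

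**Exposure and titration.** SAP 2.4.3 defines exposure as last dose minus first dose plus 1, ignoring intermittent gaps. Its only titration summary is the number (%) up-titrated to 400 mg by Visit 7 (Month 8), in the sotagliflozin group. Protocol 11.4.1.1 also planned the number (%) with an up-titration followed by a down-titration.

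**Data collected.** For each adverse event, Protocol 10.4.3 requires: "The Investigator should specify the date of onset, intensity, action taken with respect to IMP". For each confirmed temporary stop, Protocol 10.3.1 requires that "the start date and end date of the period with no IMP treatment should be recorded by the Investigator", with the stop also entered in the IRT.

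**The concern.** Safety and tolerability in the total population is a stated objective (Protocol 5.2). The usual summary of treatment-limiting intolerance is the proportion of patients whose adverse event led to discontinuation. In this trial that proportion counts the outcome the protocol tries to avoid. A patient who cannot tolerate the drug will often be reduced to one tablet, held for a time, or not up-titrated, and none of these is a permanent discontinuation.

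No SAP table would then tell a reader how many patients per arm had an adverse event that interrupted or reduced study drug, or how many were still nominally in a temporary stop when the study closed. The up-titration count does not help with comparison, because it has no placebo column.

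**Working it through.** No arithmetic on trial figures applies. The documents give no rate for temporary stops, reductions or permanent stops, so the check sets the sections side by side.

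1. **Which consequences of an adverse event are tabulated?**

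| Action on study drug | AE table by arm in SAP 2.4.5.1 | Other SAP output |
|---|---|---|
| Permanent stop | Yes: overview, and SOC/PT | Disposition by reason (2.2) |
| Temporary stop | No | None by cause; compliance (2.4.3) may reflect some |
| Dose reduction | No | None |
| Not up-titrated | No | Up-titration by Month 8, sotagliflozin only (2.4.3) |

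2. **What does the permanent-stop rate measure?** In one arm, let P be the proportion with a TEAE leading to a permanent stop. Let U be the proportion with a TEAE leading to a temporary stop or reduction but never to a permanent stop. Treatment-limiting intolerance through stopping or reducing drug is P + U. Since U cannot be negative, P is a lower bound, and Protocol 10.3 and 10.3.1 steer patients into U first. Between arms, the full difference is (P_sota − P_pbo) + (U_sota − U_pbo). The SAP reports the first bracket only. The documents do not fix the sign or size of the second.

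3. **Does exposure fill the gap?** Take first dose on day 1.
   - A patient who takes the last dose before a gap on day s, restarts on day r and has a final dose on day L gets exposure L − 1 + 1 = L. The r − s − 1 days off drug do not show.
   - A patient who stops after day s and never restarts has day s as last dose, because SAP 2.5.1 uses the last administration date on the form. Exposure is s − 1 + 1 = s, so this stop does shorten exposure.

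   Exposure therefore misses only stops that are followed by a restart. In neither case does it give a cause.

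4. **Does the protocol's titration count fill the gap?** Protocol 11.4.1.1 would capture reductions after up-titration, and 11.4.1 says exposure summaries are by treatment received. The count is not tied to an adverse event. SAP 2.4.3 does not repeat it, SAP 1.1 gives the SAP precedence where the documents differ, and SAP Appendix D does not list its removal.

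5. **Are the events themselves counted?** Yes. SAP 2.4.5 presents safety results by treatment group. All TEAEs, IMP-related TEAEs, serious TEAEs and events of special interest are tabulated whatever was done with study drug. Hypotension, dehydration, hypovolaemia and syncope are listed volume-depletion terms in SAP Appendix C.

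6. **Can the missing tables be made?** Yes. Action taken per event (Protocol 10.4.3) and interruption dates (10.3.1) are recorded.

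**The case against.** The strongest reply is that no harm goes unrecorded. A patient who pauses drug for hypotension is in the all-TEAE table, in the volume-depletion row and, if judged related, in the related-TEAE table, by arm. Protocol 10.4.3 also makes a medically relevant laboratory, vital-sign or ECG abnormality that leads to discontinuation or a dosing change reportable as an adverse event. This stands. A reader might infer from the missing tables that tolerability harm is largely uncounted by arm; the documents do not support that. Only the link from event to dosing consequence is missing.

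A reader might also infer that a stop never resumed leaves no trace. It does, through the last-dose date, as step 3 of the check shows.

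Other replies carry partial weight:
- Temporarily stopped patients are to be reassessed at every visit and reclassified once the decision is permanent (Protocol 10.3.1). This limits the number left unresolved, but nothing in the documents says how many would remain.
- SAP silence on down-titration is not clearly a cancellation of the protocol's count. That is fair, but the ambiguity is itself a reason to restate the count in the governing document.
- Protocol and SAP agree on the permanent-discontinuation category, so no analysis is broken. That is correct; the point concerns completeness of description, not validity.

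**Conclusion.** The point holds in a limited form. The SAP has no by-arm summary of TEAEs leading to temporary discontinuation or dose reduction, and its titration count has no placebo comparison. Given how the protocol handles intolerance, the permanent-discontinuation rate is likely to understate treatment-limiting intolerance.

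The size is unknown. It depends on U in each arm, for which the documents offer no figure. Expressing it as lost power would not suit either, since SAP 2.4.5 plans no hypothesis tests on safety. It may be tempting to conclude that the tolerability objective would be answered too favourably to sotagliflozin. That would require U to be larger on sotagliflozin than on placebo, and the documents do not establish this.

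The conclusion assumes that investigators follow the protocol's preference for reduction and temporary stops, and that action taken is completed on the adverse event form. No efficacy estimate is affected. This is a cheap improvement to the safety description.

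**What to change.** In SAP 2.4.5.1, next to the permanent-discontinuation table, add by treatment group and descriptively:
- TEAEs leading to temporary discontinuation of IMP, by primary SOC and PT;
- TEAEs leading to dose reduction, by primary SOC and PT.

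In SAP 2.4.3, add for both arms:
- number (%) of patients with any temporary stop;
- number (%) in an unresolved temporary stop at closeout, defined for example as a recorded start date, no restart by the closeout visit and no permanent-discontinuation page;
- number (%) up-titrated, and number (%) up-titrated then down-titrated, replacing the sotagliflozin-only count.

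The cost is a few standard tables from data already in the e-CRF and IRT. There is no new data collection, no testing and no change to patient management.

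Separately, Protocol 8.1.1.2 asks for every effort to return to the higher dose after a down-titration or temporary stop, while Protocol 10.3 says the lower dose is kept for the remaining treatment period after a reduction. The two sections must be reconciled, or the rule applied in practice stated, so that down-titration counts can be read consistently. This review takes no view on which is right.

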***Analysis of events of special interest***

The selection of PTs will be based on standardized MedDRA query (SMQ) for each corresponding item.

An overview table of EOSI, summarizing number (%) of patients with any of following categories will be provided:

- At least one TEAE EOSI by category of severe hypoglycemia, genital mycotic infection, urinary tract infection, volume depletion and events related/possible related to volume depletion, diarrhea, pancreatitis, bone fracture, venous thrombotic event, amputation, diabetic, ketoacidosis, malignancy of special interest

***Drug-induced liver injury***

These events will be presented in the same manner as EOSI.

***2.4.5.2 Analyses of laboratory variables***

Summary statistics of all laboratory variables (number, mean, standard deviation, median, first quartile, third quartile, minimum, and maximum) will be calculated for each visit or study assessment by treatment group during the treatment period.

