#### **11.4.3.3 Analysis of adverse events of special interest**

Pregnancy and symptomatic overdose with IMP will be included in overall AE summaries if any are reported. An ALT increase  $\geq 3$  x ULN will be included in laboratory PCSA summary if any.

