#### **11.4.3.5 Analysis of laboratory variable**

The number and percentage of patients with PCSA or by the predefined categories (if no PCSA criterion is defined) at any evaluation during the on-treatment period will be summarized for each clinical laboratory test within each treatment group. The summaries will include patients in the safety population who have at least 1 laboratory test performed during the on-treatment period and, when required by the definition of the abnormality, with an available Baseline value and available laboratory normal ranges.

Descriptive statistics will be used to summarize the laboratory results and the changes from Baseline by visit and for the last on-treatment value within each treatment group. Shift tables and other tabular and graphical methods may be used to present the results for laboratory tests of interest. Listings will be provided with flags indicating the out of laboratory range values as well as the PCSA values.

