##### *Liver tests*

The liver function tests, namely ALT, AST, alkaline phosphatase, and total bilirubin, are used to assess possible drug-induced liver toxicity. The proportion of patients with PCSA values at any post-baseline visit by Baseline status will be displayed by treatment group for each parameter.

The proportion of patients with PCSA values at any post-baseline visit will also be displayed by duration of exposure for each treatment group.

Time to onset of the initial ALT and AST elevation ( $>3$  x ULN) and total bilirubin elevation ( $>2$  x ULN) will be analyzed for each parameter using Kaplan-Meier estimates, using the midpoint of the time interval between the first assessment showing the elevation and the previous assessment, presented by treatment group. Consideration should be given to the impact of the spacing of scheduled tests. A graph of distribution of peak values of ALT versus peak values of total bilirubin will also be presented. Note that the ALT and total bilirubin values are presented on a logarithmic scale. The graph will be divided into 4 quadrants with a vertical line corresponding to 3 x ULN for ALT and a horizontal line corresponding to 2 x ULN for total bilirubin.

The normalization (to  $\leq 1$  x ULN or return to Baseline if Baseline  $>ULN$ ) of elevated liver function tests will be summarized by categories of elevation (3 x ULN, 5 x ULN, 10 x ULN, 20 x ULN for ALT and AST; 1.5 x ULN for alkaline phosphatase; and 1.5 x ULN and 2 x ULN for total bilirubin), with the following categories of normalization: never normalized, normalized after permanent discontinuation of study drug. Note that a patient will be counted only under the maximum elevation category.

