# 1 OVERVIEW AND INVESTIGATIONAL PLAN

## 1.1 BACKGROUND

SOLOIST is a Phase 3, multicenter, randomized, double-blind, placebo-controlled, parallel group, stratified study of sotagliflozin for the treatment of patients with worsening heart failure.

After screening, patients who met all eligibility criteria were centrally randomized via in a 1:1 ratio to sotagliflozin or placebo at randomization visit. Randomization was stratified by baseline left ventricular ejection fraction (LVEF) (LVEF<50% and LVEF≥50%) and region (North America, Latin America, Western Europe, Eastern Europe, and rest of the world).

The original plan was to randomize approximately 4000 patients. However, SOLOIST enrollment was closed in March 2020 before meeting this objective.

A recent publication in the Journal of the American College of Cardiology discussed how clinical trials and programs have been disrupted by the COVID-19 pandemic. It provided the sotagliflozin program as an example where clinical trials have been prematurely terminated. Recommendations included careful consideration of statistical issues relating to potential loss of power, increased variability in data, and challenges in adjudication of events. Similarly, the FDA has issued guidance specific to COVID-19 recognizing the potential for disruption of clinical trials and identifying some of the data and statistical issues that need to be addressed by investigators and sponsors.

This plan describes statistical efficacy analyses to be conducted by an independent academic statistician and separately verified by the Lexicon statistical team. It addresses issues related to the early termination of SOLOIST. These issues have been reviewed and the recommended steps have been chosen in a blinded fashion without the use of any unblinded interim analysis.

The termination of enrollment and follow-up of SOLOIST did not allow enough time to amend the study protocol. Changes to the intended analysis plan are reflected in this document, rather than the protocol, and this plan takes precedence where there are differences between the two documents.

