***2.4.5.3 Analyses of vital signs variables***

Summary statistics of all laboratory variables (number, mean, standard deviation, median, first quartile, third quartile, minimum, and maximum) will be calculated for each visit or study assessment by treatment group during the treatment period.

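### The SAP no longer specifies the protocol's threshold counts by arm for laboratory tests and vital signs, or its ALT-bilirubin plot, and does not log the change

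*SAP*

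**What the plan says.** **Protocol.** Section 11.4.3.5 plans, for each laboratory test and treatment group, "The number and percentage of patients with PCSA or by the predefined categories (if no PCSA criterion is defined) at any evaluation" in the on-treatment period. Section 11.4.3.6 plans the same for each vital sign. Section 11.4.3 says the count takes in every on-treatment evaluation, unscheduled and repeat samples included. Section 11.4.3.3 says an ALT rise of at least 3 x ULN "will be included in laboratory PCSA summary if any". Under Liver tests: "The proportion of patients with PCSA values at any post-baseline visit by Baseline status will be displayed by treatment group for each parameter", and "A graph of distribution of peak values of ALT versus peak values of total bilirubin will also be presented", with reference lines at 3 x ULN and 2 x ULN. That section also plans time to first elevation and normalization categories. Section 11.4.3.4 tabulates liver-related adverse events by the Hepatic disorder SMQ.

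**SAP.** Section 2.4.5.2, on laboratory variables, is one sentence: "Summary statistics of all laboratory variables (number, mean, standard deviation, median, first quartile, third quartile, minimum, and maximum) will be calculated" for each visit and arm. Section 2.4.5.3, on vital signs, repeats it and still begins "Summary statistics of all laboratory variables". Section 2.1.4.1 keeps the ALT adverse event of special interest (AESI): at least 3 x ULN if baseline is below the ULN, or at least 2 x baseline if baseline is at or above it. It also says drug-induced liver injury (DILI) will be shown as a number and percentage per arm. Section 1.1 says "this plan takes precedence where there are differences between the two documents". Among safety analyses, Appendix D logs only the move of hypoglycemia to efficacy.

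**The concern.** Laboratory and vital-sign harms usually sit in the tail: a few patients with a large ALT rise, a high potassium, a steep creatinine rise or a very low blood pressure. The usual comparison is the number of patients per arm who cross a stated limit. The protocol planned that comparison and the SAP does not mention it. If the SAP is followed as written, an excess of such patients on sotagliflozin could be seen only indirectly. The protocol itself notes an acute fall in eGFR and a population at increased risk of acute kidney injury (4.4.1), and a possible fall in blood pressure (8.9).

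**Working it through.** The plan gives no figure to reproduce. The check is a text comparison, followed by a test of whether the remaining outputs recover what is missing.

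**Step 1. Side by side.**

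| Output by arm | Protocol | SAP |
|---|---|---|
| Patients with on-treatment PCSA, each laboratory test | 11.4.3.5 | none |
| Patients with on-treatment PCSA, each vital sign | 11.4.3.6 | none |
| Patients with ALT at least 3 x ULN | 11.4.3.3, in the PCSA summary | AESI defined in 2.1.4.1, no count |
| Peak ALT against peak bilirubin | Liver tests | none |
| Time to elevation, normalization | Liver tests | none |
| Liver events | 11.4.3.4, Hepatic disorder SMQ | DILI number and percentage, no case rule |
| Per-visit descriptive statistics | 11.4.3.5, 11.4.3.6 | 2.4.5.2; 2.4.5.3 names the wrong variables |

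**Step 2. Do the per-visit minimum and maximum recover the tail?** A maximum shows one patient. It need not be the true peak either, because SAP 2.5.4 uses the last value when a window holds several. Protocol 10.3.3 calls for an immediate recheck of an abnormal value before permanent discontinuation, so a normal recheck in the same window replaces the abnormal result.

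The post-randomization windows are days 5 to 11, 12 to 18, 22 to 36 and 85 to 141. They leave days 19 to 21 (3 days) and 37 to 84 (84 - 37 + 1 = 48 days) uncovered. If Month 8 is read as Week 32, its window is 224 ± 28, or days 196 to 252, so days 142 to 195 are uncovered too. Scheduled visits within the protocol's tolerance fall inside the windows (for example 15 ± 3 is 12 to 18, and 113 ± 7 is 106 to 120). The gaps therefore affect mainly unscheduled samples, which the protocol's count would include.

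**Step 3. Do the mean, SD and quartiles recover it?** This is an illustration, not document data. Assume a fraction p of an arm goes from ALT 25 to 200 U/L at one visit.
- Mean shift = p x (200 - 25): 0.01 x 175 = 1.75 U/L; 0.02 x 175 = 3.5 U/L.
- SD added in quadrature = 175 x √(p(1 - p)): 175 x 0.0995 = 17.4 U/L; 175 x 0.14 = 24.5 U/L.
- Third quartile: if those patients were otherwise spread over the distribution, it becomes the 0.75/0.99 = 75.8th or 0.75/0.98 = 76.5th percentile of the rest, so it barely moves.
- With an assumed 500 per arm, p is 5 to 10 patients. With the 2000 per arm originally planned (4000/2), it is 20 to 40.

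The SD would react, but it does not say how many patients crossed a limit.

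**Step 4. Do the adverse event tables recover it?** An AESI is an adverse event by definition (protocol 10.4.1.3), and meeting an AESI definition is one of the criteria for recording a laboratory abnormality as an adverse event (10.4.3). Cases should therefore reach the TEAE tables in SAP 2.4.5.1. Those tables depend on investigator reporting and coding, and a preferred term does not carry the threshold, so neither branch of the ALT definition can be counted from them.

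**Step 5. Does the DILI count recover it?** DILI has no row in the SAP's identification table and no term list in Appendix C. The general statement in 2.4.5.1 that terms come from SMQs names none for the liver.

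**The case against.** **The SAP may not have removed anything.** Section 1.1 describes the plan as covering efficacy analyses, precedence applies only where the documents differ, and Appendix D is headed as key changes. Silence could mean that the protocol's safety analyses still stand. This has some force: the SAP does not expressly delete the PCSA analyses. But it has full safety sections (2.1.4 and 2.4.5), and protocol 11.4.3 ties the PCSA limits to those in effect at final SAP approval, while the SAP never mentions them. At best the status is ambiguous, and that also needs correcting.

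**A reader might infer that the ALT AESI and other outliers would appear in no table by arm.** The documents do not support that. Minimum, maximum and SD are planned by visit and arm, recorded ALT events enter the TEAE tables, and DILI gets a number and percentage.

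**A reader might also infer that blood pressure and renal decline go unanalysed.** That is not so. Change in systolic pressure is an endpoint (SAP 2.1.3.3 and 2.4.4.4), and hypotension terms are in the volume-depletion list (Appendix C), summarised as number and percentage of patients. Sustained eGFR falls are in the renal composite, and eGFR slope is a secondary endpoint.

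**Part of the remedy is new.** Protocol 11.4.3.3 sends only the 3 x ULN branch to the PCSA summary, so counting the 2 x baseline branch is an addition. A case rule for DILI may also exist in the charter of the committee described in protocol 6.4.5, which is not among the documents.

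**Conclusion.** The concern holds in this form: the SAP specifies no threshold-based count by arm of patients with ALT/AST, bilirubin, potassium, creatinine or blood-pressure outliers, although the protocol planned such counts, and Appendix D does not record the change. The ALT AESI is defined but not counted, and DILI is counted without a stated rule. The remaining outputs give partial sight of the tail but do not replace the comparison.

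No primary or secondary inference is affected, and the safety analyses are descriptive. The size of the loss cannot be computed from the documents; the ALT figures above rest on assumed values. The conclusion assumes that the SAP is followed as written and that no separate table specification outside these documents keeps the PCSA outputs. The change should be made, because it is cheap and concerns a planned safety comparison.

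**What to change.** - **SAP 2.4.5.2:** restore the number and percentage of patients per arm with any on-treatment PCSA, using all evaluations including unscheduled ones, and restore the peak ALT against peak bilirubin plot. Attach or cite the PCSA limits, which are not in the documents.
- **ALT AESI:** add a count by arm of patients meeting the definition in SAP 2.1.4.1, with the two branches shown separately.
- **DILI:** state how cases are identified, for example by the protocol's Hepatic disorder SMQ, or by the plot quadrant above 3 x ULN for ALT and 2 x ULN for bilirubin.
- **SAP 2.4.5.3:** replace the reference to laboratory variables with vital signs, and restore the vital-sign PCSA count.
- **Appendix D:** if any of these outputs is meant to be dropped, record it with a reason.

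The cost is a few standard tables and one plot from data already collected. No design change or new data collection is needed.
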